## 0.5 Study treatment

Study treatment will start with MTX 6 to 8 mg/week, which will be promptly escalated to the maximum tolerable dose (MTD)  $\leq$ 25 mg/week (the maximum dose should be set according to the package insert of each country) in line with EULAR Recommendations 2016, and will be in principle maintained at the MTD from Week 12 onward. Also, the dosage of MTX will remain unchanged from Week 20 to 24 except for dose reduction/interruption due to an adverse drug reaction (ADR).

If the dosage of MTX is maintained  $\geq 10$  mg/week and remission (SDAI  $\leq 3.3$ ) is achieved at Week 24, the MTX therapy will be continued (ARM-1).

If SDAI remission is not achieved despite the dosage of MTX is maintained  $\geq 10$  mg/week at Week 24, a bDMARDs will be added to the treatment in line with EULAR Recommendations 2016. Subjects will subcutaneously receive ADA 40 mg as a bDMARD every other week up to Week 48, and be randomized to a group in which the MTD of MTX (10 to 25 mg/week) will be maintained (ARM-2) and a group in which the dosage of MTX will be reduced to 6 to 8 mg/week (ARM-3). Then, the efficacy and safety will be evaluated. If a subject becomes intolerable to MTX  $\geq 10$  mg/week at Week 24 due to an ADR or other relevant reasons, the subject will be terminated from the study at that time. The subject will

be also terminated from the study when subjects have received a non-ADA bDMARD or JAK inhibitor.

The primary endpoint will be the SDAI remission rate at Week 48 in the ADA/MTX-MTD Group (ARM-2) and ADA/MTX-Reduced Dose Group (ARM-3). Key secondary endpoints will be the SDAI remission rate at Week 24, the SDAI remission rate at Week 48 in MTX Monotherapy Group, the modified total sharp score (mTSS) at each assessment timepoint and changes from baseline to each assessment timepoint, and ACR20, ACR50, and ACR70 response rates at each assessment timepoint. Also, the correlation of the erythrocyte MTX-PG concentration to SDAI, mTSS, and ACR-N will be exploratorily evaluated.

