## 9.2.2 Method of biomarker analysis

The biomarker analysis will be performed on FAS.

Summary statistics in each ARM will be calculated for erythrocyte MTX-PG concentrations and blood cytokine levels, as well as change from baseline and % change from baseline. Also, the correlation of SDAI, mTSS, and ACR-N to erythrocyte MTX-PG concentration will be evaluated. Furthermore, the correlation of SDAI and ACR-N to plasma microRNA will be evaluated.

For serum anti-adalimumab antibody, the frequency of and the proportion of subjects with the antibody expression will be calculated.

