2.8. Multiplicity Adjustment

Multiplicity will not be adjusted in this study.

3. Statistical Analysis Set

- 3.1. Definition of Statistical Analysis Set
- 3.1.1. Full analysis set (FAS)

FAS is defined as a group of subjects who receive study drug (MTX) and have evaluable efficacy data at 1 or more time points following the administration of study drug (including subjects who discontinued the study before Week 24 as well as those randomized to ARM-1, 2 or 3).

Modified FAS (mFAS) is defined as a group of subjects who are randomized after Week 24, receive study drug (ADA), and have evaluable efficacy endpoint at 1 or more time points following the administration of study drug (only the subjects randomized to ARM-2 or 3).

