3.2. Statistical Analysis Set for Each Endpoint

The analysis of primary efficacy endpoint will be performed on mFAS as the main analysis set, and on PPS as a supplementary analysis set. All other efficacy and exploratory analyses will be performed exclusively on FAS. Meanwhile, the analysis of safety variables will be performed on the Safety Analysis Set.

4. Analysis Plan of Subject Disposition and Overall Exposure

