7.2. Analysis Plan of Clinical Laboratory Values and Vital Signs

For continuous variables, descriptive statistics of measurements at each assessment timepoint and their changes from baseline will be calculated for each ARM (ARM-1, 2, and 3). Furthermore, analysis of covariance (ANCOVA) adjusted by country will be performed to make a comparison between ARM-2 and ARM-3, and calculate the estimate of difference between the treatment arms and its two-tailed 95% confidence interval. In addition, descriptive statistics will be calculated, being stratified by country.

As an order categorical variable, clinical laboratory values will be categorized to Lower than the reference (L), Within the reference (N), and Higher than the reference (H), and then the number and proportion of subjects by L, N, and H will be presented in a shift table (baseline vs. each visit during treatment) for each ARM (ARM-1, 2, and 3). In addition, the maximum and minimum values after the start of treatment will be presented in a shift table for comparison with baseline. Furthermore, Wilcoxon rank sum test will be performed to make a comparison between ARM-2 and ARM-3.

Descriptive statistics of vital signs (diastolic blood pressure, systolic blood pressure, pulse rate, body temperature) and body weight at each assessment timepoint and their changes from baseline will be computed for each ARM (ARM-1, 2, and 3). Furthermore, analysis of covariance (ANCOVA) adjusted by country will be performed to make a comparison between ARM-2 and ARM-3, and calculate the estimate of difference between the treatment arms and its two-tailed 95% confidence interval.

8. Analysis Plan of Exploratory Endpoints

8.1. Erythrocyte MTX-PG Concentration at Weeks 0, 4, 8, 12, 24, 36, and 48 Descriptive statistics for erythrocyte MTX-PG concentrations as well as change from baseline and change rate from baseline will be calculated by country. In addition, descriptive statistics for Week 24 onward will be calculated at each assessment timepoint for each ARM (ARM-1, 2, and 3).

Pearson's product-moment correlation coefficient, Spearman's rank correlation coefficient, and their 95% confidence interval will be calculated at each assessment timepoint to evaluate the correlation of exposure to MTX, SDAI, mTSS, and ACR-N to erythrocyte MTX-PG concentration. Furthermore, cutoff values for AST increased, ALT increased, and WBC decreased, and their differences among the participating countries will be discussed.

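### After Week 24 the MTX-PG correlations have no ARM split or adjustment, so a pooled coefficient could show a small association that exists in no arm

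*SAP*

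**What the plan says.** SAP 8.1 treats MTX-PG in two steps. For the summaries it names the arms: "descriptive statistics for Week 24 onward will be calculated at each assessment timepoint for each ARM (ARM-1, 2, and 3"). For the association it plans Pearson and Spearman coefficients with 95% confidence intervals, which "will be calculated at each assessment timepoint to evaluate the correlation of exposure to MTX, SDAI, mTSS, and ACR-N to erythrocyte MTX-PG concentration". That sentence names no ARM, country or other adjustment. Protocol 9.2.2 has the same structure: the summary statistics are by ARM, and then "the correlation of SDAI, mTSS, and ACR-N to erythrocyte MTX-PG concentration will be evaluated".

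The analysis set does not separate the arms either. SAP 3.2 states: "All other efficacy and exploratory analyses will be performed exclusively on FAS". SAP 3.1.1 describes the FAS as "including subjects who discontinued the study before Week 24 as well as those randomized to ARM-1, 2 or 3".

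Protocol 0.5 and 6.1 define the arms at Week 24. ARM-1 is the subjects in SDAI remission, who stay on MTX alone. The non-remitters are randomized to ARM-2 (MTX 10 to 25 mg/week) or ARM-3 (MTX 6 to 8 mg/week), and in both "Subjects will subcutaneously receive ADA 40 mg as a bDMARD every other week up to Week 48".

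MTX-PG is measured at Weeks 0, 4, 8, 12, 24, 36 and 48. Hand and foot X-rays for mTSS are taken at screening, Week 24 and Week 48 or early termination (Protocol 7.2.1), so no Week 36 mTSS is scheduled.

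**The concern.** After Week 24, ARM bears on both sides of the correlation. It sets the MTX dose, and so MTX-PG, because ARM-3 is cut by design. It also bears on disease activity, because ARM-1 is selected for low SDAI while ARM-2 and ARM-3 are non-remitters given a second drug. A coefficient computed across all three arms picks up the differences between arm means as well as any relation between subjects treated alike.

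The likely direction is negative: ARM-1 has higher MTX-PG and lower SDAI than ARM-3. That would read as higher MTX-PG going with lower disease activity, which is what Protocol 2.2.1 reports from earlier work, so it could be taken as confirmation. The relation of MTX-PG to efficacy and safety is part of the objective in Protocol 3.2 and SAP 1.

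**Working it through.** The documents state no figure for the correlation analysis and no spread for MTX-PG or SDAI. The arm mix can be derived from the plan. The rest is assumption, shown as ranges.

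1. **Plan's own figure.** Protocol 9.4.1 expects 15% remission on MTX and 10% unable to stay at 10 mg/week or more. Enrolment for 220 randomized is 220 / (0.85 × 0.90) = 287.6, so the stated 288 reproduces.

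2. **Arm mix from 300 enrolled.** ARM-1: 300 × 0.90 × 0.15 = 40.5. ARM-2 and ARM-3: 300 × 0.90 × 0.85 / 2 = 114.75 each. Use 40/115/115, N = 270, ignoring later dropout.

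3. **Closed form, zero correlation in every arm.** Let *a* be the amount by which ARM-3 MTX-PG is lower and *b* the amount by which ARM-1 SDAI is lower, each in within-arm SDs. SDAI is equal in ARM-2 and ARM-3. With arm shares p1 = 40/270 = 0.148 and p3 = 115/270 = 0.426:

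   r = -a·b·p1·p3 / √{[1 + a²·p3(1 - p3)] · [1 + b²·p1(1 - p1)]}

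   For a = b = 1: r = -0.0631 / √(1.2445 × 1.1262) = -0.053. Fisher z: atanh(-0.053) × √267 = -0.87, so the 95% interval excludes 0 in about 14% of trials.
   - For a from 0.5 to 2 and b from 0.5 to 1.5, r runs from -0.015 to -0.12, and the interval excludes 0 in 6% to 50%.
   - At the highest Week 24 remission rate cited in Protocol 9.4.1 (29.3%), 270 × 0.293 = 79 are in ARM-1 and about 96 in each other arm. Then a = b = 1 gives r = -0.085 and 29%. The full range is -0.02 to -0.19 and 7% to 87%, the top needing both gaps at their largest.

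4. **Simulation with skewed data.** Gamma distributions, independent within arm, 40/115/115. Mean MTX-PG is 100/100/60 with CV 40%. For comparison, 7 mg against the 12.7 mg/week mean dose cited in Protocol 6.1.1 is a ratio of 0.55. Mean SDAI is 9 in ARM-2 and ARM-3 and 2.5 to 5 in ARM-1, with CV 40% to 100%.
   - Pooled Spearman: about -0.03 to -0.11, p < 0.05 in about 8% to 46% of trials.
   - Pooled Pearson: p < 0.05 in about 7% to 40%.
   - Partial rank correlation adjusted for ARM: p < 0.05 in 4% to 6%.
   - Mean SDAI equal in all arms: no artefact, rejection at about the nominal 5%.

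5. **Where in that range is plausible.** Protocol 9.4.1 assumes 30% remission in ARM-2 and ARM-3. With mean SDAI 9 and CV 100% (an exponential), P(SDAI ≤ 3.3) = 1 - exp(-3.3/9) = 31%, close to that. At CV 40% (gamma shape 6.25) it is only about 2%. The high end therefore rests on an SDAI spread that fits the Protocol's assumption poorly. At CV 100% the Spearman rate is about 19% with ARM-1 mean SDAI 2.5 and about 8% with mean 5. A lognormal simulation set to 30% remission in ARM-2 and ARM-3 and 50% to 80% (assumed) in ARM-1 gives Spearman -0.03 to -0.09 (7% to 29%) and Pearson -0.015 to -0.05 (5% to 14%).

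6. **Precision after the change.** The half-width of the 95% interval at r = 0 is tanh(1.96/√(n - 3)): 0.31 for n = 40, 0.18 for n = 115, and 0.12 for N = 270.

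No separate calculation was made for mTSS or ACR-N. The same argument applies wherever their means differ between arms.

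**The case against.** The SAP is silent on ARM here; it does not order pooling, and by-ARM output is not excluded. That is true, but by-ARM wording is used for the MTX-PG summaries in the same section and again in SAP 8.2 and 8.4. The natural reading of the correlation sentence is one coefficient per visit.

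The analysis is exploratory, no decision rests on it, and the correlations up to Week 24 address MTX therapy directly. This stands, and it limits the weight of the point. So does the size: coefficients of this order would not by themselves support a claim that MTX-PG drives efficacy.

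A reader might infer a much larger problem by also letting SDAI be worse in ARM-3 than in ARM-2. That case should not be counted. ARM-2 and ARM-3 are randomized to MTX dose, so a worse SDAI in ARM-3 would be a real effect of the reduction, and an association arising from it is at least partly genuine. With equal SDAI in those two arms, the artefact comes only from including ARM-1.

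Conditioning on ARM also has a price. It sets aside the randomized ARM-2 versus ARM-3 contrast, the one part of the MTX-PG variation that is not observational. This is fair, but the by-ARM efficacy comparisons already report that contrast.

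**Conclusion.** The point holds, within limits. Followed as written, SAP 8.1 gives coefficients at Weeks 36 and 48 (mTSS: Week 48 only) that mix a remission-selected group on MTX alone with two ADA-treated groups on different MTX doses. With no relation inside any arm, the pooled coefficient can still be slightly negative and cross the 5% level more often than it should, by the amounts in the simulation above. Those figures rest on assumed arm gaps and spreads and on the planned arm mix; the lower part of the range agrees better with the Protocol's 30% remission assumption.

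A reader might infer that the study would answer its MTX-PG objective wrongly. The documents do not support that: five of the seven MTX-PG timepoints fall at or before Week 24, where pooling is sound, and the later by-ARM summaries would let a careful reader see the mixture. The later coefficients could mislead; they need not. The primary non-inferiority analysis is not affected.

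**What to change.** Add to SAP 8.1:

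- For Week 36 (SDAI, ACR-N) and Week 48 (SDAI, mTSS, ACR-N), compute the Pearson and Spearman coefficients within ARM-1, ARM-2 and ARM-3 separately.
- Give one overall summary per visit: a partial rank correlation adjusted for ARM and country. Country is the stratification factor, and SAP 8.1 already describes MTX-PG by country.
- Label any coefficient pooled across arms after Week 24 as descriptive.
- Keep the pooled coefficients up to and including Week 24.

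The cost is a few lines of SAP text and by-ARM programming. The statistical downsides should be stated. Per-ARM intervals are wider, most of all in ARM-1, although the adjusted summary keeps nearly the pooled precision. The 6 to 8 mg/week range in ARM-3 restricts any within-arm correlation involving MTX exposure. The within-ARM coefficients remain observational and do not use the randomized dose contrast.

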9.1. Revision from Protocol

Date	Name	Addresses for distribution	Revised contents
Not applicable			

9.2. Revision History of the Statistical Analysis Plan

Date	Name	Addresses for distribution	Revised contents
7/27/2021	[name]		 Add wording that a missing data on the final scheduled visit will be imputed with data on End of Study for a sensitivity analysis of primary endpoint Update title of PI Typographical correction Update statistical software version

10. Organization and Environment for Statistical Analyses

10.3. Software Environment

.

Statistical analyses described in this Statistical Analysis Plan will be conducted, and Tables, Figures, and Lists will be prepared using SAS version 9.4 on Windows 10 or above. The analyses results will be available as PDF file, Microsoft Word 2016 Rich Text Format, or Excel 2016 Worksheet. The use of any statistical software other than SAS or selfdeveloped software should be specified in the Statistical Analysis Report if applicable. Validations for SAS programs that are prepared for individual analyses will not be conducted.

11. Signature

I hereby guarantee that the contents of this Statistical Analysis Plan are appropriate for "MIRACLE (Methotrexate inadequate response patient with Rheumatoid Arthritis treated by Adalimumab in combination with Low-dose Methotrexate) Study", and this Statistical Analysis Plan was finalized before the final data analysis.

Day/Month/Year

(Seal)
